7.2.4 Other reportable events

Other reportable events of this trial are:

- a new cancer (that is not a condition of the study);
- an AE associated with an overdose.

7.2.5 Unexpected Adverse Event

An unexpected adverse event is any adverse drug event, the specificity or severity of which is not consistent with the current version of the Investigator's Brochure of Pembrolizumab. Also, reports which add significant information on specificity or severity of a known, already documented adverse event constitute unexpected adverse events. An event more specific or more severe than described in the reference safety document would be considered "unexpected".

A suspected unexpected serious adverse reaction (SUSAR) is a serious adverse reaction, the nature, or severity of which is not consistent with the applicable reference safety document. All suspected adverse reactions related to the IMP which occur in the concerned trial and that are both unexpected and serious (SUSARs) are subject to expedited reporting.

7.2.6 Overdose

For subjects treated with pembrolizumab an overdose will be defined as any dose of 1,000 mg or greater (exceeding 5x the protocol prescribed dose).

7.3 Assessment of relationship - Adverse drug reaction

The causal relationship to study drug is determined by a physician and should be used to assess all adverse events (AE). The causal relationship can be one of the following:

- Related: There is a reasonable causal relationship between study drug administration and the AE.
- Not related: There is not a reasonable causal relationship between study drug administration and the AE.

The term "reasonable causal relationship" means there is evidence to suggest a causal relationship.

In case of a missing causality assessment in the eCRF or SAE reporting form, the event will be regarded as "probably related" unless further specified.

A serious ADR (SADR) is an adverse drug reaction that meets the definition of a serious event (provided below).

7.4 Assessment of severity

Intensity of adverse events will be graded using the National Cancer Institute Common Terminology Criteria for Adverse Events (CTCAE), version 4.03.

If an adverse event occurs which is not contained in the CTCAE version 4.03, the fivepoint scale below will be used.

Grade 1:	Mild; asymptomatic or mild symptoms; clinical or diagnostic observations only; intervention not indicated
Grade 2:	Moderate: minimal, local or noninvasive intervention indicated; limiting age-appropriate instrumental ADL
Grade 3:	Severe or medically significant but not immediately life- threatening; hospitalization or prolongation of hospitalization indicated; disabling; limiting self-care ADL
Grade 4:	Life-threatening consequences; urgent intervention indicated

Grade 5: Death related to AE

7.5 Safety recording and reporting requirements

7.5.1 Recording periods

- Adverse events are recorded from time of signed informed consent until 6 weeks (EoT visit) after surgery.
- Serious adverse events are recorded from time of signed informed consent until 90 days after last dose of IMP or for 6 weeks after surgery if the subject initiated new anticancer therapy (e.g. radio-chemotherapy)
- Pregnancies occurring in a study subject are recorded from time of signed informed consent until 120 days after last dose of IMP.

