- 18. Other active malignancy requiring treatment

Exceptions include basal cell carcinoma of the skin or squamous cell carcinoma of the skin that has undergone potentially curative therapy or in situ cervical cancer.

19. Lactating or pregnant women, women of child-bearing potential who do not agree to the usage of highly effective contraception methods (allowed

methods of contraception, meaning methods with a rate of failure of less than 1% per year are implants, injectable contraceptives, combined oral contraceptives, intrauterine pessars (only hormonal devices), sexual abstinence or vasectomy of the partner). Women of childbearing potential must have a negative pregnancy test (serum β -hCG) at Screening.

- 20. Any psychiatric illness that would affect the patient's ability to understand the demands of the clinical trial
- 21. Patient has already been recruited in this trial
- 22. Patient who has been incarcerated or involuntarily institutionalized by court order or by the authorities § 40 Abs. 1 S. 3 Nr. 4 AMG.
- 23. Patients who are unable to consent because they do not understand the nature, significance and implications of the clinical trial and therefore cannot form a rational intention in the light of the facts [§ 40 Abs. 1 S. 3 Nr. 3a AMG].

5 Schedule of Assessment and Procedures

Please refer to the Schedule of Assessments for an overview.

Data will be collected via an electronic Case Report Form (eCRF) for each eligible patient. The investigator should confirm eligibility of the patient according to the inclusion and exclusion criteria of the study. All patients will provide written Informed Consent before any study specific assessment is performed. A study specific assessment is defined as a procedure that is not part of the routine assessments performed for diagnostic purposes or standard care. Screening assessments should occur within 28 days of the first administration of study drug.

Patients not meeting the inclusion/exclusion criteria will not be enrolled into the study. Patients should receive their first dose of study treatment as soon as possible after they have been intended to be treated with study medication.

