5.3 Removal of Patients from Treatment

Patients will be free to discontinue treatment or withdraw from the study at any time, for any reason, or they may be withdrawn/removed if necessary, to protect their health (see reasons for withdrawal below). It is understood by all concerned that an excessive rate of withdrawals can render the study uninterpretable; therefore, unnecessary withdrawal of patients should be avoided. Patients that will be withdrawn from the study will not be replaced.

Patients will be removed from further treatment for the following reasons:

- Disease progression
- Continued unacceptable toxicities despite optimal treatment or dose reduction
- During the treatment a delay of study treatment of more than 6 weeks
- Delay from screening to start of study treatment of more than 31 days
- Intercurrent illness, at the investigator's discretion
- Withdrawal of consent

- Non-compliance / Lost to follow-up
- Pregnancy
- Termination of the study by the sponsor

If there is a medical reason for withdrawal of treatment, the patient will remain under the supervision of the investigator until the AEs have been resolved or declined to baseline values.

If a patient has failed to attend scheduled assessments in the study, the investigator must determine the reasons and circumstances as completely and accurately as possible.

In case of premature discontinuation of the study treatment, the investigations scheduled for the EOT and the Follow-up visits should be performed, if possible. In any case, the eCRF section entitled "End of Treatment" must be completed.

Should a patient decide to withdraw, all efforts will be made to complete and report the observations as thoroughly as possible. The investigator should contact the patient to determine as completely as possible the reason for the withdrawal. A complete final evaluation at the time of the patient's withdrawal should be made with an explanation of why the patient is withdrawing from the study. If the reason for removal of a patient from the study is an adverse event or an abnormal laboratory test result, the principal specific event or test will be recorded on the eCRF.

If a patient withdraws consent for further study treatment, the patient should still be followed for progression and survival. If a patient withdraws consent for further participation in the study, follow-up assessments will be discontinued.

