1.3 Endpoints

- 1.3.1 Primary Endpoint
 - Frequency and severity of AEs including peri- and post-operative complications (grade 2-4 AEs according to NCI-CTCAE V4.03)
 - o number of patients treated in compliance with protocol
 - Tumor response evaluation

clinical response parameters:

- o response rates (Δ tumor size / lymph node size), according to RECIST 1.1 criteria
- Δ PET-activity (standardized uptake value [SUV]) (analysis of this end point is not covered in this SAP)
 Pathologic response parameters:
- Pathologic regression grading according to Junker criteria (see Appendix 3 of CSP)
- 1.3.2 Secondary Endpoints
 - disease free survival
 - overall survival

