2.11.3 Safety population

The safety population consists of all patients who received at least one dose of study medication.

If the Safety and ITT Population are identical (i.e. all enrolled patients received at least one dose of treatment medication) the analysis will be performed for the Safety Population and the ITT Population together, labelled with "Safety/ITT Population".

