6.2.1 Data Points

- Adverse Event Overview
 - o Any AE
 - Any AE of clinical interest
 - o Any related AE
 - o Any severe AE
 - Any AE grade 2-4
 - Any related severe AE
 - o Any related AE grade 2-4
 - o Any SAE
 - Any related SAE
 - Any AE requiring study treatment dose modification
 - o Any AE requiring study treatment discontinuation
- Adverse Events by maximum severity
 - o Any AE
 - o Any related AE
- Adverse Event by highest relationship
 - o Any AE
 - o Any AE grade 2-4

Adapted from:

STAT03_A Statistical Analysis Plan Version 6.0, Effective Date 16-Feb-2018

Confidential and intellectual property of Assign DMB. No part of this document or its contents may be duplicated, referenced, published or otherwise disclosed in any form or by any means without prior written consent of Assign DMB.

- o Any SAE
- Adverse Events by SOC and preferred term
 - o Any AE
 - Any related AE
 - Any AE grade 2-4
 - o Any related AE grade 2-4
 - Any SAE
 - Any related SAE
 - Any AE requiring study treatment discontinuation
- 6.2.2 Definition
 - Severe AE: AEs with severities of Grade 3-5 (severe or medically significant, severe or life threatening, death) will be considered as severe AEs
 - Missing causality assessment for adverse events will lead to handling of the AE as "related", see Section 7.3 of the CSP.

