6.2.3 Inferential Analysis

AE summary tables will provide the number and percentage of patients with AEs and the 95 % confidence intervals for the event rates according to Wilson.

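### AE tables have no onset condition, so events that began before the first dose count in the primary grade 2–4 AE rate and in the any-AE and any-SAE rates

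*Protocol*

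**What the plan says.** **Recording.** Protocol 7.5.1 states: "Adverse events are recorded from time of signed informed consent until 6 weeks (EoT visit) after surgery". For serious events it states: "Serious adverse events are recorded from time of signed informed consent until 90 days after last dose of IMP". The schedule of assessments marks adverse events at the screening visit.

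**Length of the pre-dose period.** The introduction to protocol section 5 states: "Screening assessments should occur within 28 days of the first administration of study drug". Protocol 5.3 lists as a reason for removal: "Delay from screening to start of study treatment of more than 31 days".

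**Endpoint.** SAP 1.3.1 gives the primary safety endpoint as "Frequency and severity of AEs including peri- and post-operative complications (grade 2-4 AEs according to NCI-CTCAE V4.03"). It has no onset condition.

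**Analysis.** SAP 2.1 has the main analysis summarise everything recorded up to the snapshot. SAP 2.11.3 states: "The safety population consists of all patients who received at least one dose of study medication". SAP 6.2.3 states: "AE summary tables will provide the number and percentage of patients with AEs", with Wilson 95% intervals. SAP 6.2.1 and Tables 14.4.1–14.4.4 list any AE, any AE of grade 2–4, any SAE and their related counterparts, none with an onset condition. SAP 6.2.2 contains two definitions only. One is for severe AEs. The other begins "Missing causality assessment for adverse events will lead to handling of the AE as" and ends with the word related. The list of changes in SAP 2.14 adds no onset rule.

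**The concern.** The safety population selects patients, not events. Once a patient has had one dose, everything recorded since consent enters the tables, including events that started and ended before any study drug was given. The primary objective is the feasibility and safety of neoadjuvant pembrolizumab. An event that began before the first dose and did not worsen says nothing about the safety of the drug, or of surgery after the drug.

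The trial has no control arm to show how much of a reported rate is background. The error also has one direction: adding pre-dose events can raise the number of patients with at least one event but never lower it. In the maximum-severity tables a pre-dose episode of higher grade would also displace a later, milder episode of the same event, because protocol 8.4.4 counts repeated episodes once, at the worst grade.

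The protocol already draws this line elsewhere. For events of clinical interest, section 7.5.2 separates the time from consent to treatment start from the time after it. The SAP does not carry the distinction into the AE tables.

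**Working it through.** **1. The plan's own figures.** With N = 30, the event rate seen at least once with 95% probability is 1 − 0.05^(1/30) = 9.50%, as stated. The exact intervals in protocol Table 3 reproduce when x = 30 × rate is used, for example 97.4% gives 83.9–100.0, 37.2% gives 20.4–56.7 and 10% gives 2.1–26.5. Nothing below changes these figures.

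**2. Is there an onset filter anywhere?** No rule in SAP 2.1, 2.11.3, 2.14, 6.2.1–6.2.3 or 7.1.4, or in protocol 8.4.1 and 8.4.4, restricts events by start date. The term treatment emergent occurs once, in the protocol's rationale for two cycles, and is not an analysis rule there.

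**3. How long is the pre-dose period?** EOT is about Day 88–102 (discharge on Day 60–74 plus about 4 weeks).
- 28 days of screening: 28/(28 + 102) = 21.5% to 28/(28 + 88) = 24.1% of AE recording time.
- 31 days: 31/133 = 23.3% to 31/119 = 26.1%.
- An assumed 7 days from consent to first dose: 7/109 = 6.4% to 7/95 = 7.4%.
- SAEs, with dose 2 on Day 21 and recording to 90 days later (Day 111): 28/(28 + 111) = 20.1%.

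These are shares of calendar time, not of events.

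**4. Effect per patient.** With 30 treated patients, one patient whose only qualifying event is pre-dose adds 1/30 = 3.3 points. As an illustration with assumed counts, 12/30 is 40.0% (Wilson 24.6–57.7). One such patient gives 13/30 = 43.3% (27.4–60.8). Three give 15/30 = 50.0% (33.2–66.8).

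**5. Effect by table.** Let p be the rate from events after the first dose and q the share of patients with a qualifying pre-dose event, assumed independent of later events. The reported rate is p + (1 − p)q. The documents give no q, so the values are assumptions.

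| Rate | p | q = 5% | q = 10% |
|---|---|---|---|
| Any AE | 97.4% (reference) | 97.5% | 97.7% |
| Any SAE | 37.2% (reference) | 40.3% | 43.5% |
| Grade 2–4 AE | 40% (assumed) | 43% | 46% |
| Grade 2–4 AE | 80% (assumed) | 81% | 82% |

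For any AE at q = 10%, the expected number of added patients is 30 × 0.026 × 0.10 = 0.08.

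**6. Missing causality.** If one pre-dose SAE with a blank causality field survived to the analysis, a related-SAE count of 3/30 = 10.0% (3.5–25.6) would become 4/30 = 13.3% (5.3–29.7). This needs several unlikely steps, discussed under the objection.

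**The case against.** **The AE definition might exclude these events.** Protocol 7.2.1 uses the ICH wording about a subject who has been given a product. But 7.5.1 and the schedule expressly record from consent, and no analysis rule applies the narrower reading. This does not stand.

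**A reader might infer that about a quarter of the reported AEs predate treatment.** The documents do not support that. The 28 days are a maximum for screening assessments, and section 5 asks for the first dose as soon as possible. The time after dosing contains two infusions and a lung resection, so a share of days says little about a share of events. A general inflation of several points across all tables does not follow either: at the 97.4% reference rate, any AE has only 2.6 points of room. This stands as a limit on the size.

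**A reader might infer that pre-dose events will be reported as drug-related.** The missing-causality rule has no onset exception, so it is possible on paper. But protocol 7.5.2 makes relatedness a mandatory investigator entry, protocol 7.3 adds a proviso to its default, and data are cleaned before the snapshot. Blank fields should be rare, so this is a marginal consequence.

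**Entry rules and population limit the number of events.** Eligibility criteria exclude many acute conditions, some assessments are repeated if older than 7 days, and patients who are never dosed are outside the safety population. This stands, and reduces the expected count.

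**No decision rests on the AE rate.** The stopping rule and the feasibility criterion concern resection, the analysis is descriptive, and start dates are listed. This stands in part: a careful reader could find pre-dose events in the listings, but the tabulated percentages and intervals would still include them.

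**Conclusion.** The gap is real. Followed as written, the plan puts pre-dose events in treated patients into the primary grade 2–4 AE rate and the any-AE and any-SAE rates, and the effect is upward only. Its size cannot be calculated, because the documents give no pre-dose event rate. What can be said is 3.3 points per treated patient whose only qualifying event is pre-dose, assuming 30 treated. That is negligible for any AE and potentially visible for grade 2–4 AEs and SAEs. Even there the shift is likely to be small beside the sampling uncertainty: the Wilson interval at 12/30 spans 57.7 − 24.6 = 33.1 points. It is nevertheless a systematic error that a date condition removes. All values of q, the base rates of 40% and 80%, and the patient counts are assumptions. Recording AEs from consent is not the problem; only the tabulation is.

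**What to change.** In SAP 6.2.2, define a treatment-emergent AE as one with a start date on or after the date of the first dose. Include a worsening of a pre-dose event where it is recorded as a new AE entry. A general rule for worsening in grade should not be promised, because Listing 16.2.4.2 shows one CTCAE grade per event and no date of grade change.

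Use treatment-emergent AEs in Tables 14.4.1–14.4.4 and list pre-dose AEs in treated patients separately. Peri- and post-operative complications all start after the first dose and stay in. Add one sentence on incomplete start dates, for example that such an event counts as treatment-emergent unless the known part of the date places it before the first dose. Restrict the rule on missing causality to treatment-emergent events. Record the definition in SAP 2.14.

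The cost is one SAP definition, one derivation and one extra listing. AE start dates and infusion dates are already collected (Listings 16.2.4.2 and 16.2.4.1), so no new data are needed. The only downside is that reported AE rates may be slightly lower.

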2.4 Primary endpoint

- frequency and severity of adverse events including peri- and post-operative complications (grade 2-4 AEs according to NCI-CTCAE V4.03)
 - number of patients treated in compliance with protocol
- tumor response evaluation

clinical response parameters:

- o response rates (∆ tumor size / lymph node size), according to RECIST
 1.1 criteria
- $\circ \Delta$ PET-activity (standardized uptake value [SUV])

Pathologic response parameters:

• Pathologic regression grading according to Junker criteria [12]

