3.2 End of Treatment

End of Treatment is defined as 6 weeks post surgery (approx. 4 weeks post discharge). In patients who discontinue during the treatment phase, an End of Treatment (EOT) visit will be performed within 28 days after treatment discontinuation.

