 For the time period beginning at start of treatment through 6 weeks following surgery, any ECI, or follow up to an ECI, whether or not related to IMPs, must be reported within 24 hours of investigators awareness to safety desk.

Other reportable events: For each patient any 'other reportable' event occurring until 6 weeks after surgery must be reported immediately (within 24 hours) after investigator's awareness to the safety desk.

Pregnancy: Pregnancies occurring during study treatment and up to 120 days after last dose must be reported by the investigator on the **Pregnancy Report Form** within 24 hours after awareness to the safety desk.

Follow up case reports have to be provided as new information becomes available. If an SAE is experienced in addition to or related to the pregnancy e.g. an induced or spontaneous abortion, also an SAE Report has to be sent to the safety desk within 24 hours / GCP-V § 12(4) after first knowledge.

Overdose: If an adverse event(s) is associated with ("results from") the overdose of IMP, the adverse event(s) is reported as a **serious adverse event**, even if no other seriousness criteria are met. An SAE Report has to be sent to the safety desk within 24 hours of investigators awareness.

If an overdose is administered without any associated clinical symptoms or abnormal laboratory results, the overdose is reported as a **non-serious Event of Clinical Interest** (ECI), using the terminology "accidental or intentional overdose without adverse effect." An SAE Report has to be sent to the safety desk within 24 hours of investigators awareness.

Abnormal Laboratory results: Abnormal laboratory test results will be recorded on the laboratory results pages of the eCRF. Laboratory-test-value abnormalities should additionally be considered an AE in case they are:

- 1. Accompanied by clinical symptoms
- 2. Leading to a change in study medication (e.g. dose modification, interruption or permanent discontinuation)
- 3. Requiring a change in concomitant therapy (e.g. addition of, interruption of, discontinuation of, or any other change in a concomitant medication, therapy or treatment)

In general it is the investigator's responsibility to review all abnormal laboratory results and to determine if a given value represents a clinically significant change compared to previously obtained values and results in an Adverse Event or not.

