2. GENERAL CONSIDERATIONS

2.1 Conduct of Analysis

Two analyses will be performed for this study.

- Main analysis will be performed after all patients had their end of treatment, data entry for all visits except the follow-up visits is complete, data were cleaned, a Data Review Meeting was performed and database snapshot has been completed.
- Addendum analysis will be performed after last patient completed the entire study, follow-up data entry and cleaning are complete and database was closed.

Main analysis will summarize all data recorded up to the time of the database snapshot. Addendum analysis will only present data captured during follow-up. This means, the addendum analysis may only include overall survival, end of study details and subsequent cancer therapy. An SAE listing will also be prepared to show possible follow-up information of SAEs ongoing after end of treatment.

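### Adverse-event recording ends at a surgical anchor, so patients never operated on get a shorter window than operated patients but enter the same crude primary AE rates

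*Protocol*

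**What the plan says.** Protocol 2.4 lists as a primary endpoint the "frequency and severity of adverse events including peri- and post-operative complications", restricted to grades 2-4. The recording periods are as follows.

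- **AEs (7.5.1):** "Adverse events are recorded from time of signed informed consent until 6 weeks (EoT visit) after surgery".
- **SAEs (7.5.1 and schedule footnote 7):** "until 90 days after last dose of IMP or for 6 weeks after surgery if the subject initiated new anticancer therapy".
- **ECIs (7.5.2):** "For the time period beginning at start of treatment through 6 weeks following surgery, any ECI" is reportable.
- **Other reportable events (7.5.2):** an "event occurring until 6 weeks after surgery must be reported immediately".

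EOT for operated patients is 6 weeks after surgery, about 4 weeks after discharge (3.2). The only fallback is also in 3.2: "In patients who discontinue during the treatment phase, an End of Treatment (EOT) visit will be performed within 28 days after treatment discontinuation". Section 7.5.1 does not refer to it. Follow-up (5.2.6) covers drug-related AEs that continue from treatment and does not collect new non-serious ones.

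The safety population is everyone who received at least one dose (protocol 8.3.3, SAP 2.11.3). SAP 6.2.3 reports the number and percentage of patients with AEs and Wilson intervals. It sets no observation window and makes no allowance for differing follow-up. SAP 2.1 fixes the timing: "Main analysis will be performed after all patients had their end of treatment".

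**The concern.** Patients without surgery are foreseen. Section 3.1 sends progression or intolerable toxicity straight to EOT and follow-up, the feasibility criterion in 8.1 tolerates up to 20% without timely resection, and 5.4 has a stopping rule on the same event. For these patients the anchor that closes AE recording does not occur.

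If the EOT visit stands in for it, their window closes weeks earlier than that of operated patients. They then count in the same denominator as if fully observed. The subgroup is not random, because toxicity and progression are reasons for losing surgery. Section 6.3.1 itself warns that immune-related events can appear months after the last dose. At stake is how far the primary AE percentages can be read as rates over one defined period.

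**Working it through.** **The plan's own figures.** The observation limit in 8.2 reproduces: 1 - 0.05^(1/30) = 9.50%. So does Table 3's interval for the 73.7% drug-related AE rate at N=30: Clopper-Pearson with 0.737 × 30 = 22.11 events gives 54.5-88.0%. Neither is disputed.

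**Window ends, from the visit schedule** (V2 Day 21 ± 3, pre-surgery Day 43-50, discharge Day 60-74; no dosing delay assumed).

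| Patient | Rule | AE window ends |
|---|---|---|
| Operated, surgery at pre-surgery date | 43 + 42 to 50 + 42 | Day 85-92 |
| Operated, via discharge | 60 + 28 to 74 + 28 | Day 88-102 |
| Stopped at V2, not operated | 18 + 28 to 24 + 28 | Day 46-52 at latest |
| Stopped at pre-surgery, not operated | 43 + 28 to 50 + 28 | Day 71-78 at latest |

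Against Day 85-102, a patient stopped at V2 is closed 33-56 days earlier (85 - 52 to 102 - 46). One stopped at pre-surgery is closed 7-31 days earlier (85 - 78 to 102 - 71). For the same pre-surgery decision day the gap is at least 42 - 28 = 14 days. The 28 days are a maximum, so real gaps can be larger.

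**SAEs without new therapy.** Ninety days after the last dose is Day 91 (only the Day 1 dose given) or Day 111 (second dose on Day 21). This is defined for every treated patient.

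**Effect on a crude rate (illustration).** Assumptions: 6 of 30 unoperated (0.20 × 30), constant hazard, and a true full-window rate r = 0.737. For a window of d days out of T, the rate seen is q = 1 - (1 - r)^(d/T), and the pooled rate is 0.8r + 0.2q.

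| d | T | q | Pooled | Shortfall |
|---|---|---|---|---|
| 49 | 88 | 52.5% | 69.5% | 4.2 points |
| 49 | 102 | 47.4% | 68.4% | 5.3 points |
| 78 | 88 | 69.4% | 72.8% | 0.9 points |
| 78 | 102 | 64.0% | 71.8% | 1.9 points |

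The shortfall is thus about 1-5 points. At the outermost window ends it is 0.6 (d = 78, T = 85) to 5.7 (d = 46, T = 102). The standard error at N=30 is √(0.737 × 0.263/30) = 8.0 points, so 5.3 points is 0.66 of one standard error.

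**If 3 of the 6 lost surgery through related toxicity**, they already count as having a related AE and truncation cannot remove it. The shortfall becomes 0.1 × (r - q), which is 0.1 × (0.737 - 0.694) = 0.4 to 0.1 × (0.737 - 0.474) = 2.6 points.

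**The case against.** The strongest reply is that this is a wording matter with little numerical effect. Much of that stands.

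- **Undefined windows.** A reader might infer that AE recording has no end for any unoperated patient. The documents do not support that. Section 7.5.1 ties the AE window to the EoT visit, and 3.1 and 3.2 give early stoppers one. What remains for them is a shorter window.
- **Both doses, no resection.** A reader might infer that these patients have no EOT at all, so that the SAP 2.1 trigger cannot be met. Surgery is numbered 3.1.1 under the treatment phase, 5.2.8 places the end of that phase at the EOT visit, and 5.3 requires the eCRF end-of-treatment section in any case. On that reading they fall under the 28-day rule and the trigger is met. The schedule, however, shows the treatment phase as V1 and V2 with pre-surgery in a separate column, so the ambiguity is real.
- **Serious late toxicity.** It is largely covered. Without new therapy the 90-day limit applies, and 7.5.2 also asks for any SAE during the study. It can be argued that this default stands when surgery never occurs, but the exception as written has no end date in that case.
- **ECIs.** The list in 7.2.3 holds only asymptomatic overdose and one liver-test pattern, so little late immune toxicity is lost through that route.
- **Bias.** Under 8.4.4 each patient counts once per event at worst grade, so a patient who lost surgery through related toxicity is already counted in the any-related-AE rate.
- **Inputs.** The 73.7% covers all grades and has no stated observation length, whereas the endpoint specifies grades 2-4. The tolerated 20% includes delayed resections, and those patients are operated.

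The reply does not remove the core point. Under the stated rules, a foreseen and selected subgroup gets a shorter window for a primary endpoint, and follow-up does not collect the new non-serious events that fall after it.

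**Conclusion.** The concern holds in a limited form. Patients never operated on have AE, ECI and other-reportable-event recording that closes by about Day 46-52 or Day 71-78, against about Day 85-102 for operated patients. The EOT rule is ambiguous for those unresected after both doses, and the SAE exception after new therapy lacks an end date without surgery. The SAP pools these unequal windows.

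The effect on an any-AE rate is modest: about 1-5 points under the assumed inputs (6 of 30 unoperated, constant hazard, 73.7%), and about 0.4-2.6 points if half of the six lost surgery through related toxicity. A reader might infer that the safety conclusion is materially biased. The figures do not support that, being small beside Table 3's 54.5-88.0% interval. The main loss is late, non-serious grade 2-4 events, and the documents give no rate from which to size it. This is a cheap improvement to the plan, not a flaw that invalidates it.

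**What to change.** **Protocol 7.5.1, 7.5.2, 3.2 and schedule footnote 7.** For patients without surgery, record AEs, ECIs and other reportable events until 90 days after the last dose, matching the existing SAE limit. State that the 90-day SAE limit applies to them whether or not new anticancer therapy starts. State in 3.2 that the 28-day EOT visit also applies to patients who complete both doses but are not resected.

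**SAP.** Apply a common analysis cut-off counted from first dose, or report observation time and AE rates by operated status. This is needed because 90 days after a Day 21 dose is Day 111, which is 9-26 days beyond operated patients (111 - 102 to 111 - 85). Without it the imbalance would reverse. If the protocol can no longer be amended, the SAP step can still be taken.

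**Cost.** A short amendment and, in about 6 patients under the assumption above, one contact about 90 days after the last dose. SAE recording already implies that contact, but the planned visits do not supply it: first follow-up is 3 months after EOT, about Day 140 for an EOT on Day 49. Some AEs of replacement therapy will be collected; the causality field and start dates separate them.
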